2.2 Preclinical Studies

The activity of CDX-011 in pediatric tumors was recently investigated through the Pediatric Preclinical Testing Program. GPNMB gene expression was evaluated in a variety of solid tumor and leukemia xenograft models. Given the consistent expression of GPNMB in the osteosarcoma xenografts, the *in vivo* anti-tumor activity was investigated in 6 female CB-17SC mice bearing osteosarcoma. The mice received 2.5 mg/kg of CDX-011 IV weekly for 3 doses, followed by 3 weeks of observation. Complete tumor responses were seen in 3/6 osteosarcoma xenografts. Of the 3 responding xenografts, 2 had the highest levels of GPNMB expression. The lowest GPNMB-expressing osteosarcoma xenograft had minimal response to CDX-011 treatment (Figure 1).^{[23,45](#)} GPNMB protein expression through immunohistochemistry and by enzyme-linked immunosorbent assay (ELISA) has

also been assessed in human osteosarcoma cell lines. Sixty-seven human osteosarcoma samples were tested and 92.5% of osteosarcoma samples expressed GPNMB. CDX-011 induced cytotoxic effects in 74% of osteosarcoma cell lines and GPNMB protein levels correlated with CDX-011 *in vitro* cytotoxicity.⁴⁶

[figure not shown]

Figure 1. CDX-011 *in vivo* objective response activity for osteosarcoma models. Kaplan-Meier curves for EFS (left), median relative tumor volume graphs (center), and individual tumor volume graphs (right) are shown for selected lines. Treated (black lines), statistical significance (P values) of the difference between treated and control groups are included.

2.3

In this trial a tumor sample to test for GPNMB expression by immunohistochemistry (IHC), similar to the previous breast cancer and melanoma clinical trials, will be required. This will allow us to determine if higher levels of GPNMB expression by IHC correlates with tumor response to CDX-011 in osteosarcoma patients.

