9.7 Statistical Considerations for Secondary Aim 1.2.3

9.7.1 *To determine the relationship of GPNMB expression by IHC to response in tumor specimens from patients:* Submission of archival tissue will be required for this study. The primary cohort to address this aim will be the patients who were not previously treated with eribulin. The GPNMB expression IHC result will be coded as an integer between 0 and 3 with 0 being no GPNMB expression and 3 indicating strong GPNMB expression. The outcome measure will be DC success (Yes v. No). Logistic regression using the categorical IHC result will be fitted to the data. The fitted coefficients from the logistic regression, and the p-value for the test of the hypothesis of no relationship between IHC result and probability of DC success will be used to characterize this secondary analysis. Trend will also be assessed using the actual IHC numerical value.

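### Section 9.7.1 reports the GPNMB aim through four-category logistic coefficients that will often not be finite with at most 29 patients; a penalised fit with a named test would repair this

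*Combined protocol and SAP*

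**What the plan says.** Section 9.7.1 takes patients without prior eribulin as the main cohort, codes GPNMB staining as an integer from 0 to 3, and uses DC success, yes or no, as the outcome. It then states: "Logistic regression using the categorical IHC result will be fitted to the data". The reported results are "The fitted coefficients from the logistic regression, and the p-value for the test of the hypothesis of no relationship" between staining and DC success, and these "will be used to characterize this secondary analysis". A second analysis is added: "Trend will also be assessed using the actual IHC numerical value".

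The section names no estimator, test, reference category or rule for sparse or empty categories. Section 9.1 caps the cohort at 29 evaluable patients; the stage I rule in Section 9.2 can end it at 19.

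The background expects an ordered relation. Section 2.2 reports that "The lowest GPNMB-expressing osteosarcoma xenograft had minimal response to CDX-011 treatment" and that "GPNMB protein levels correlated with CDX-011" cytotoxicity in vitro. The text under heading 2.3 asks whether "higher levels of GPNMB expression by IHC correlates with tumor response to CDX-011 in osteosarcoma patients".

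**The concern.** A logistic model with one parameter per category reproduces each category's observed success proportion. If that proportion is 0 or 1, the fitted log odds run to minus or plus infinity and the software prints whatever value it reached when it stopped. With 29 patients over four categories, and an uninteresting DC rate of 0.20 (about 6 successes), such a category is likely. If it is also the reference category, every contrast fails.

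The coefficients are one of the two quantities the section names to characterise the aim. The other, the p-value, depends on a test still to be chosen, and the candidates behave very differently under separation. What is at stake is how the biomarker question is answered and reported. The activity decision in Section 9.2 is untouched.

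**Working it through.** **Inputs.** n = 29 (Section 9.1) and 19 (Section 9.2). DC rates 0.20 and 0.42 (Section 9.2) and 0.12 (the historical 4-month event-free rate, Section 2.1). Section 2.2 reports expression in 92.5% of preclinical samples, which suggests 7.5% at score 0. The division over scores 1 to 3 is not given, so it is assumed:

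- A: 25% each
- B: 7.5% at score 0, the rest equal
- C: 7.5/15/30/47.5%
- D: 7.5/47.5/30/15%
- a fifth case: three equal categories, nobody at score 0

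**The plan's own figure.** Section 9.7.1 states no sample size or power. The nearest figure on the same n and DC rates is the two-stage table in Section 9.2. With Pr(S|R) = 0.90, the probabilities of concluding that the drug is effective come out at 0.108, 0.949, 0.904 and 0.789, against the stated 0.11, 0.95, 0.904 and 0.79. It reproduces.

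**Chance of a non-finite coefficient, no association.** With category shares q_k and DC rate p, the chance that no occupied category is all-or-none is n! times the coefficient of x^n in the product over k of [exp(q_k x) − exp(q_k p x) − exp(q_k(1−p)x) + 2].

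Hand check for split A, p = 0.20, n = 29. The all-failure terms are 4(0.95)^29 − 6(0.90)^29 + 4(0.85)^29 − (0.80)^29 = 0.9037 − 0.2826 + 0.0359 − 0.0015 = 0.6555. Adding all-success categories and removing empty ones adds 0.002, giving 0.658.

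| n | DC rate | A | B | C or D | three equal, no score 0 |
|---|---|---|---|---|---|
| 29 | 0.12 | 0.892 | 0.914 | 0.936 | 0.676 |
| 29 | 0.20 | 0.658 | 0.769 | 0.823 | 0.360 |
| 29 | 0.42 | 0.192 | 0.499 | 0.588 | 0.043 |
| 19 | 0.20 | 0.874 | 0.868 | 0.899 | 0.629 |
| 19 | 0.42 | 0.542 | 0.648 | 0.740 | 0.210 |

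**Score 0 alone, at 7.5%.** Expected count 29 × 0.075 = 2.2; empty with probability 0.925^29 = 0.10. Occupied and all-or-none at p = 0.20: 0.985^29 + 0.94^29 − 2(0.925)^29 = 0.645 + 0.166 − 0.208 = 0.60. At p = 0.42 it is 0.46. If score 0 is the reference, all contrasts are then non-finite.

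**Stage I gate.** The table does not condition on it. With P(R) = 0.05 assumed and DC rate 0.20, trials that reach 29 patients show separation in 50-75%; averaged over both stopping points it is 76-86%. At 0.42 only about 4% of trials stop at 19.

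**With a real gradient, n = 29, splits A-D.** DC rates over scores 0 to 3:

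- 0.05/0.12/0.30/0.55: 85-92%
- 0.10/0.25/0.45/0.60: 61-83%
- 0.25/0.35/0.45/0.55: 30-67%

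**Illustration.** Successes 0/2, 2/9, 3/9, 4/9. Ordinary coefficients against score 0 are about 19 to 20 with standard errors near 12,500, so a Wald z is about 20/12,500 = 0.002. The likelihood-ratio statistic is 2.57 on 3 df, p = 0.46. A Firth fit of this model adds one half to successes and failures in each occupied category. The score 0 log odds become ln(0.5/2.5) = −1.61, and the contrasts are 0.51, 0.99 and 1.41. The trend slope is 0.64 (SE 0.48) by ordinary likelihood and 0.57 (SE 0.46) by Firth.

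**Tests.** At n = 29 the four-category likelihood-ratio test has type I error of about 6-8% at DC rates 0.20 and 0.42. An ordinary trend fit can also separate: with no association at 0.20, in 1-4% of trials at n = 29 and 8-14% at n = 19. The Firth slope was finite in every simulated trial, with penalised likelihood-ratio type I error of 2.4-4.6%.

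The penalised four-category test applies the usual statistic to the augmented counts. In the illustration these are 0.5/3, 2.5/10, 3.5/10 and 4.5/10, pooled 11/33, giving 2 × (0.211 + 0.164 + 0.006 + 0.292) = 1.35, p = 0.72. Simulating that formula (20,000 trials per cell, n = 29, splits A-D) gave type I error of 1.4-3.4% at 0.20 and 0.42. For the steepest gradient its power was 19-34%, against 37-57% for the ordinary likelihood-ratio test.

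**The case against.** The strongest reply is that separation is a fault of the estimator, not of the model. The plan already pairs an overall test with a trend, which is a defensible combination. This stands. A reader might infer that the trend should replace the categorical analysis, but the documents do not support that. The preclinical results suggest ordering without establishing a linear step per score, and the comparison depends on the pattern. At n = 29, likelihood-ratio against score-trend power is:

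- steepest gradient above: 37-57% v 52-68%
- present versus absent (0.05 v 0.45): 12-48% v 8-31%
- inverted U (0.10/0.45/0.45/0.10): 27-48% v 2-18%
- threshold at score 2 (0.10 v 0.45): about equal

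A second reply is that every probability rests on an assumed split. This also stands, and the three-category case shows how mild the problem can be. Section 15.1.1 is not shown and text around heading 2.3 is missing, so the absence of a sparse-category rule can be asserted only of the visible text.

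Third, the plan names no Wald test. The near-zero Wald power found in simulation (1-3% for the steepest gradient) comes from setting separated log odds at ±20. It describes a worst case and is not the plan's performance.

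Finally, a statistician would notice an infinite coefficient beside 0/2. That limits the harm, but the remedy would then be chosen after the data are seen.

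**Conclusion.** The concern holds as a point about estimator and test. If 9.7.1 means ordinary maximum likelihood, at least one four-category coefficient will be non-finite at n = 29 in 66-82% of trials at a DC rate of 0.20 and 19-59% at 0.42. This assumes four occupied score levels with splits A-D, no association and no conditioning on the gate. With three equal categories it is 36% and 4%.

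Two stronger readings go too far. One is that the fit nearly always fails when expression matters: the range over rising gradients is about 30-92%, and 85-92% belongs to the steepest one only. The other is that the aim would have no usable p-value: the likelihood-ratio p-value remains computable and is only somewhat liberal.

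The point is minor to moderate. Power is modest by any method, the aim is secondary, and no go/no-go rule uses it. It merits a change because the remedy uses the same data and is almost all wording.

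**What to change.** In Section 9.7.1:

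- Keep both the categorical and the 0-3 trend analyses, and fit both by Firth penalised logistic regression.
- Take p-values from penalised likelihood-ratio tests and intervals from the profile penalised likelihood, so that test and interval agree. State that Wald tests will not be used.
- Name the reference category, and say that an empty category is dropped with its degree of freedom; penalisation does not help there.
- Tabulate DC successes over patients for each score.
- Label the analysis exploratory.

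Leading with the trend is optional; if chosen, say so before data are seen.

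Cost: wording, and software that fits the penalised model. Firth estimates are generally pulled somewhat toward no effect, and for a category of one or two patients the penalty dominates: 0/2 is fitted as 0.5/3 = 17%. The penalised trend test is slightly conservative. The penalised four-category test is more so, as shown in the working. A sponsor unwilling to give up that power could name the ordinary likelihood-ratio test for the overall p-value, accepting its 6-8% type I error and occasional disagreement with the Firth intervals.

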9.8 Gender and Minority Accrual Estimates

The gender and minority distribution of the study population is expected to be:

Racial Categories	Ethnic Categories				Total
	Not Hispanic or Latino		Hispanic or Latino		
	Female	Male	Female	Male	
American Indian/ Alaska Native	0	0	0	0	0
Asian	0	0	0	0	0
Native Hawaiian or Other Pacific Islander	0	0	0	0	0
Black or African American	2	6	0	0	8
White	9	17	1	3	30
More Than One Race	0	0	0	0	0
Total	11	23	1	3	38

This distribution was derived from ADVL0821, ADVL0921, ADVL1221.

10.0 EVALUATION CRITERIA

10.1 Common Terminology Criteria for Adverse Events (CTCAE)

This study will utilize version 4.0 of the CTCAE of the National Cancer Institute (NCI) for toxicity and performance reporting. A copy of the CTCAE version 4.0 can be downloaded from the CTEP website

(http://ctep.cancer.gov/protocolDevelopment/electronic_applications/ctc.htm).

Additionally, toxicities are to be reported on the appropriate case report forms.

Please note: 'CTCAE v4.0' is understood to represent the most current version of CTCAE v4.0 as referenced on the CTEP website (ie, v4.02 and all subsequent iterations prior to version 5.0).

10.2

Response Criteria for Patients with Solid Tumors

For the purposes of this study, patients should be evaluated for response following Cycles 2, 4 and 6 and following every 3rd cycle thereafter. Patients who have a RECIST response (CR or PR) at Cycle 6 will have confirmatory imaging after Cycle 8.

Response and progression will be evaluated in this study using the new international criteria proposed by the revised Response Evaluation Criteria in Solid Tumors (RECIST) guideline (version 1.1).⁵¹ Changes in the largest diameter (unidimensional measurement) of the tumor lesions and the shortest diameter in the case of malignant lymph nodes are used in the RECIST criteria.

10.2.1 Disease Parameters

10.2.1.1 Measurable disease: Measurable lesions are defined as those that can be accurately measured in at least one dimension (longest diameter to be recorded) as ≥ 20 mm by chest x-ray, as ≥ 10 mm with CT scan, or ≥ 10 mm with calipers by clinical exam. All tumor measurements must be recorded in millimeters (or decimal fractions of centimeters).

10.2.1.2 Malignant lymph nodes: To be considered pathologically enlarged and measurable, a lymph node must be ≥ 15 mm in short axis when assessed by CT scan (CT scan slice thickness recommended to be no greater than 5 mm). At baseline and in follow-up, only the short axis will be measured and followed.

10.2.1.3 Non-measurable disease: All other lesions (or sites of disease), including small lesions (longest diameter <10 mm or pathological lymph nodes with ≥ 10 to <15 mm short axis), are considered non-measurable disease. Bone lesions, leptomeningeal disease, ascites, pleural/pericardial effusions, lymphangitis cutis/pulmonitis, inflammatory breast disease, and abdominal masses (not followed by CT or MRI), are considered as non-measurable.

Note: Cystic lesions that meet the criteria for radiographically defined simple cysts should not be considered as malignant lesions (neither measurable nor non-measurable) since they are, by definition, simple cysts.

'Cystic lesions' thought to represent cystic metastases can be considered as measurable lesions, if they meet the definition of measurability described above. However, if non-cystic lesions are present in the same patient, these are preferred for selection as target lesions.

10.2.1.4 Target lesions: All measurable lesions up to a maximum of 2 lesions per

organ and 5 lesions in total, representative of all involved organs, should be identified as **target lesions** and recorded and measured at baseline. Target lesions should be selected on the basis of their size (lesions with the longest diameter), be representative of all involved organs, but in addition should be those that lend themselves to reproducible repeated measurements. It may be the case that, on occasion, the largest lesion does not lend itself to reproducible measurement in which circumstance the next largest lesion which can be measured reproducibly should be selected. A sum of the diameters (longest for non-nodal lesions, short axis for nodal lesions) for all target lesions will be calculated and reported as the baseline sum diameters. If lymph nodes are to be included in the sum, then only the short axis is added into the sum. The baseline sum diameters will be used as reference to further characterize any objective tumor regression in the measurable dimension of the disease.

10.2.1.5 **Non-target lesions**: All other lesions (or sites of disease) including any measurable lesions over and above the 5 target lesions should be identified as **non-target lesions** and should also be recorded at baseline. Measurements of these lesions are not required, but the presence, absence, or in rare cases unequivocal progression of each should be noted throughout follow-up.

10.2.2 **Methods for Evaluation of Measurable Disease**

All measurements should be taken and recorded in metric notation using a ruler or calipers. All baseline evaluations should be performed as closely as possible to the beginning of treatment and never more than 4 weeks before the beginning of the treatment.

The same method of assessment and the same technique should be used to characterize each identified and reported lesion at baseline and during follow-up. Imaging-based evaluation is preferred to evaluation by clinical examination unless the lesion(s) being followed cannot be imaged but are assessable by clinical exam.

10.2.2.1 **Clinical lesions**: Clinical lesions will only be considered measurable when they are superficial (eg, skin nodules and palpable lymph nodes) and ≥ 10 mm diameter as assessed using calipers (eg, skin nodules). In the case of skin lesions, documentation by color photography, including a ruler to estimate the size of the lesion, is recommended.

10.2.2.2 **Chest x-ray**: Lesions on chest x-ray are acceptable as measurable lesions when they are clearly defined and surrounded by aerated lung. However, CT is preferable.

10.2.2.3 **Conventional CT and MRI**: This guideline has defined measurability of lesions on CT scan based on the assumption that CT slice thickness is 5 mm or less. If CT scans have slice thickness greater than 5 mm, the minimum size for a measurable lesion should be twice the slice thickness. MRI is also acceptable in certain situations (eg, for body scans).

Use of MRI remains a complex issue. MRI has excellent contrast, spatial, and temporal resolution; however, there are many image acquisition variables involved in MRI, which greatly impact image quality, lesion conspicuity, and measurement. Furthermore, the availability of MRI is variable globally. As with CT, if an MRI is performed, the technical specifications of the scanning sequences used should be optimized for the evaluation of the type and site of disease. Furthermore, as with CT, the modality used at follow-up should be the same as was used at baseline and the lesions should be measured/assessed on the same pulse sequence. It is beyond the scope of the RECIST guidelines to prescribe specific MRI pulse sequence parameters for all scanners, body parts, and diseases. Ideally, the same type of scanner should be used and the image acquisition protocol should be followed as closely as possible to prior scans. Body scans should be performed with breath-hold scanning techniques, if possible.

10.2.2.4 Ultrasound: Ultrasound is not useful in assessment of lesion size and should not be used as a method of measurement. Ultrasound examinations cannot be reproduced in their entirety for independent review at a later date and, because they are operator dependent, it cannot be guaranteed that the same technique and measurements will be taken from one assessment to the next. If new lesions are identified by ultrasound in the course of the study, confirmation by CT or MRI is advised. If there is concern about radiation exposure at CT, MRI may be used instead of CT in selected instances.

10.2.2.5 Endoscopy, Laparoscopy: The utilization of these techniques for objective tumor evaluation is not advised. However, such techniques may be useful to confirm complete pathological response when biopsies are obtained or to determine relapse in trials where recurrence following complete response (CR) or surgical resection is an endpoint.

10.2.2.6 Cytology, Histology: These techniques can be used to differentiate between partial responses (PR) and complete responses (CR) in rare cases (eg, residual lesions in tumor types, such as germ cell tumors, where known residual benign tumors can remain).

The cytological confirmation of the neoplastic origin of any effusion that appears or worsens during treatment when the measurable tumor has met criteria for response or stable disease is mandatory to differentiate between response or stable disease (an effusion may be a side effect of the treatment) and progressive disease.

10.2.3 Response Criteria

10.2.3.1 Evaluation of Target Lesions

Complete Response (CR): Disappearance of all target lesions. Any pathological lymph nodes (whether target or non-target) must have

reduction in short axis to <10 mm.

Partial Response (PR):

At least a 30% decrease in the sum of the diameters of target lesions, taking as reference the baseline sum diameters.

Progressive Disease (PD):

At least a 20% increase in the sum of the diameters of target lesions, taking as reference the smallest sum on study (this includes the baseline sum if that is the smallest on study). In addition to the relative increase of 20%, the sum must also demonstrate an absolute increase of at least 5 mm. (Note: the appearance of one or more new lesions is also considered progression).

Stable Disease (SD):

Neither sufficient shrinkage to qualify for PR nor sufficient increase to qualify for PD, taking as reference the smallest sum diameters while on study.

10.2.3.2 Evaluation of Non-Target Lesions

Complete Response (CR):

Disappearance of all non-target lesions and normalization of tumor marker level. All lymph nodes must be non-pathological in size (<10 mm short axis).

Non-CR/Non-PD:

Persistence of one or more non-target lesion(s) and/or maintenance of tumor marker level above the normal limits

Progressive Disease (PD):

Appearance of one or more new lesions and/or *unequivocal progression* of existing non-target lesions. *Unequivocal progression* should not normally trump target lesion status. It must be representative of overall disease status change, not a single lesion increase.

Although a clear progression of “non-target” lesions only is exceptional, the opinion of the treating physician should prevail in such circumstances, and the progression status should be confirmed at a later time by the review panel (or Principal Investigator).

10.2.3.3 Evaluation of Best Overall Response

The best overall response is the best response recorded from the start of the treatment until disease progression/recurrence (taking as reference for progressive disease the smallest measurements recorded since the treatment started). The patient's best response assignment will depend on the achievement of both measurement and confirmation criteria.

For Patients with Measurable Disease (ie, Target Disease)

Target Lesions	Non-Target Lesions	New Lesions	Overall Response	Best Overall Response when Confirmation is Required*
CR	CR	No	CR	≥ 4 wks. Confirmation**
CR	Non-CR/Non-PD	No	PR	≥ 4 wks. Confirmation**
CR	Not evaluated	No	PR	
PR	Non-CR/Non-PD/not evaluated	No	PR	
SD	Non-CR/Non-PD/not evaluated	No	SD	documented at least once ≥ 4 wks. from baseline**
PD	Any	Yes or No	PD	no prior SD, PR or CR
Any	PD***	Yes or No	PD	
Any	Any	Yes	PD	

*See RECIST 1.1 manuscript for further details on what is evidence of a new lesion. **Only for non-randomized trials with response as primary endpoint. ***In exceptional circumstances, unequivocal progression in non-target lesions may be accepted as disease progression.
 
Note: Patients with a global deterioration of health status requiring discontinuation of treatment without objective evidence of disease progression at that time should be reported as “symptomatic deterioration.” Every effort should be made to document the objective progression even after discontinuation of treatment.
				

For Patients with Non-Measurable Disease (ie, Non-Target Disease)

Non-Target Lesions	New Lesions	Overall Response
CR	No	CR
Non-CR/non-PD	No	Non-CR/non-PD*
Not all evaluated	No	not evaluated
Unequivocal PD	Yes or No	PD
Any	Yes	PD

* ‘Non-CR/non-PD’ is preferred over ‘stable disease’ for non-target disease since SD is increasingly used as an endpoint for assessment of efficacy in some trials so to assign this category when no lesions can be measured is not advised
		

